## Clinical Study Protocol

### Zr-TLX250-003

Version: 8.0  
Date: 01-Apr-2022

The IMP will be shipped at room temperature (15°C to 30°C) inside an appropriately shielded container.

Upon receipt at site, Zr-TLX250 solution for IV administration will be kept in a secure, temperature-controlled, restricted-access location and in accordance with applicable regulatory requirements at the radiopharmacy of the site. The IMP should be stored at ambient temperature (15°C to 30°C) without freezing, and should be used by the expiration date and time printed on the label.

Zr-TLX250 doses will be accompanied by an individual certificate of analysis for each batch. Upon verification of the correct radioactive dose, as specified by the study protocol, the radiopharmacist will hand over the investigational product in a syringe, kept in a lead-shielded container, to the nuclear medicine investigator, or a designated and suitably qualified deputy for administration. This syringe will be labelled by the radiopharmacist according to institutional standards.

Storage, handling and destruction must be performed according to local guidelines regarding radioactive waste management. Details are outlined in the IMP Handling Manual.

#### 5.1.6.2 Drug Accountability

The investigator (or radiopharmacist, whatever applicable in certain countries) will confirm receipt of the study drug by telefax or the method given in the IMP Handling Manual and will use the study drug only within the scope of this clinical study and in accordance with this study protocol. He / she will keep a record of the dispensed study drug.

Receipt, distribution and return of the study drug must be properly documented on the forms provided by the sponsor giving the following information: study protocol number, sender, receiver, date, mode of transport, quantity, batch number, expiration date and retest date, if applicable.

The coordinating clinical research organization (CRO) will monitor the drug accountability records at regular points during the study and will perform drug reconciliation at the end of the study.

## 5.2 Treatment Assignment

Once full establishment of eligibility by the site, the screening physician will confirm eligibility. Imaging day must be scheduled before the administration of the study drug after which, the individual patient number will be allocated.

Upon patient number assignment, the authorized site representative for the study can order the study drug through the "Zr-TLX250 clinical trial IMP Order Form" in the IMP Handling Manual.

More details on the procedure are given in the IMP Handling Manual.

### **5.3 Blinding**

This is an open-label study.

### **5.4 Treatment Compliance**

Zr-TLX250 will be administered by study personnel at the site. Details of each administration will be recorded in the eCRF.

#### **Treatment of Overdose**

Zr-TLX250 has a very favourable safety profile.

The risk of overdosing is minimal in this trial, as individual doses will be prepared centrally by a radiopharmaceutical contract manufacturer. Nevertheless, if accidental overdosing of radio-labelled product should occur, it will result in increased radioactive tissue exposure, with kidney and bone marrow as the critical organs.

In the event of an overdose of Zr-TLX250, no specific treatments are available, and the patient should be treated at the discretion of the investigator.

### **5.5 Radiation Precautions**

Medical administration of radioactive diagnostic tracers such as Zr-TLX250 is guided by national radiation safety regulations, differing extensively between countries.

Excretion limits acceptable for discharge will be defined by the investigators in compliance with the local regulations. Commonly, patients will be discharged from the hospital 2 hours p.a., unless the investigator decides otherwise.

Patients will be encouraged to increase fluid intake and to void frequently through the first day after administration.

The following safety precautions apply for patients:

- Patients should be advised to observe rigorous hygiene in order to avoid risk of contamination of others using the same toilet facility.
- A double toilet flush is recommended.
- Patients should wash their hands thoroughly every time after using the toilet.
- During the first week after treatment, patients should follow detailed instructions, as given in the trial participant card, regarding their distance from and contact to other persons.

The following precautions apply for health care workers and for laboratory assessments:

Healthcare personnel are advised to limit the time of close contact with patients injected with (Zr)-labelled radiopharmaceuticals. Use appropriate shielding on the day of administration. Laboratory assessments will be performed by the central laboratory. Because of the potential for radioactivity in some blood and urine samples, the site personnel must adhere to their SOPs and/or any guidance and regulations for handling radioactive substances. It is mandatory to use protective high quality (latex/nitrile) gloves in any direct contact with the radiopharmaceutical (vial/syringe) and with the patient.

Please also refer to the IMP Handling Manual.

## **6 Therapies other than Study Treatment**

### **6.1 Prior and Concomitant Therapy**

Prior medications (within 30 days from planned dosing visit at Day 0) and all medications (including herbal medications) taken from Day 0 until EOS must be recorded in the patient's eCRF.

Treatment (concomitant medication or physical therapy) for AEs must be recorded in the AE section of the patient's eCRF.

The reason for treatment, generic name, administration form, strength, dose, frequency of dosing, route of administration, start date and, if applicable, stop date should also be recorded in the eCRF. All therapies and medications will be encoded according to the World Health Organization Drug Dictionary classification.

#### **6.1.1 Prohibited Medication**

The following medications and therapies are prohibited, and patients will be withdrawn from the study if one of the following is administered during study participation. However, patients can be included when the respective washout period before enrolment into the study is considered (Table 3).

**Table 3 Prohibited Concomitant Medication**

Drug / Therapy	Washout Period (before first administration of study drug)
Any radiopharmaceutical	10 half-lives of the radionuclide
Any other experimental diagnostic or therapeutic IMP	4 weeks
Any chemo-, radio- or immunotherapy	4 weeks
Exposure to murine or chimeric antibodies	5 years

Planned antineoplastic therapies are not allowed for the study period between administration of study drug and imaging.

### **6.1.2 Permitted Concomitant Medication**

Vitamins, herbal preparations and other nutritional supplements are permitted during this study but must be recorded.

At each visit, the investigator will ask the patient whether any medication was taken since the previous visit.

Other therapy considered necessary for the patient's health and well-being may be given at the discretion of the investigator.

Patients are allowed to be vaccinated against COVID-19; the recommendation is for the patient to be asymptomatic and have recovered from any side effects prior to infusion. The vaccine must be listed as a concomitant medication.

Patients with co-morbidities such as hypertension and other chronic medical conditions requiring ongoing medications need to stay on their medications, unless they are part of the list of forbidden medication as listed above.

## **6.2 Post-Study Therapy**

Following completion of this study, the patients will be treated according to clinical practice at the discretion of the investigator. This includes treatment of the tumour disease as well as any conditions that may arise during the trial. Description of these conditions and treatments will be provided in the study report as appropriate.

Patients who received study PET imaging, but do not have adequate surgical material to analyse may be followed-up by further imaging at the discretion of the investigator, in the best interest of the patient.

## **7 Schedule of Evaluations and Visit Description**

### **7.1 Schedule of Evaluations**

A detailed schedule of events is presented in Table 1

For time points when more than one procedure is scheduled, the assessments will be performed in an order as clinically appropriate (e.g. pre-dose schedule assessments in following order: vital signs, blood sampling for haematology and clinical chemistry, urine sampling, 12-lead ECG).

Concomitant medication and adverse events (AEs) will be recorded continuously from Day 0 until EOS.

### **7.2 Screening**

Screening is to take place between 30 days and 1 day before (-30 days to -1 day) administration of Zr-TLX250 on Day 0. Evidence of an IRM must be given from pre-study standard of care imaging (based on national standards), conducted within 90 days of Day 0 (Day -90 to Day -1), but before any screening procedure is performed.

After signing the informed consent form, patients will undergo the following screening investigations and procedures:

- Review of inclusion/exclusion criteria
- Medical history
- Physical exam
- Vital signs
- Haematology
- Serum chemistry
- Urinalysis (Dipstick)
- Pregnancy test from serum (for premenopausal female patients)
- 12-lead ECG
- Concomitant medications
- Baseline findings
- HACA testing

## 7.3 Treatment (Day 0)

The following examinations and procedures will be performed on Day 0:

### 7.3.1 Pre-dose

- Update of medical history
- Vital signs
- Haematology
- Serum chemistry
- Urinalysis (Dipstick)
- Pregnancy test from urine (for premenopausal female patients) within 24 hours before administration
- 12-lead ECG
- Concomitant medication
- Baseline findings

### 7.3.2 Administration of Study Drug (Time-point 0)

Administration of Zr-TLX250 will be slowly conducted over a minimum of 3 minutes via the IV route (see Section 5.1.4).

### 7.3.3 Time-points 0.5 and 1 Hours p.a.

- Vital signs
- Concomitant medications
- Adverse event monitoring

### 7.3.4 Time-point 2 Hours p.a.

- Vital signs
- 12-lead ECG which can be conducted at 2h ± 5 mins after administration of the IMP.
- Concomitant medication
- Adverse event monitoring

## 7.4 Imaging (Day 5 ± 2 Days, but not sooner than 72 hours p.a.)

As part of PET/CT hybrid acquisition, abdominal PET static and low dose CT including the kidneys will be performed. In case of unexpected evidence of disseminated disease (N1, M1) on imaging, patients may have an additional whole body PET/CT scan from skull base to mid-thigh at the discretion of the treating clinician for complete staging.

- Zr-TLX250 PET/CT imaging
  - Abdominal static PET/CT using low dose CT without contrast agent in a single bed position using an acquisition time of 20 minutes to maximise image quality.
  - Optional additional whole body PET/CT imaging (skull base to mid-thigh) using 6-8 bed positions with 10 minute acquisition time per bed position in case of unexpected evidence of disseminated disease (N1, M1). The additional scan if requested by the treating physician needs to be completed on Day 5 ± 2 post administration of the investigational product.
- Haematology
- Serum chemistry
- Urinalysis (Dipstick)
- Concomitant medications
- Adverse event monitoring

## 7.5 Surgery (Until Day 90 p.a.)

- Pre-scheduled partial or total nephrectomy as standard of care, open or laparoscopic, as locally established (to be performed any time after imaging, but no longer than 90 days p.a. and image acquisition). In patients who have foci of extra-renal radioactivity accumulation, a biopsy of the most accessible lesion may be carried out instead of the planned nephrectomy.
- Central histology of the renal mass or extra-renal lesion to characterise ccRCC/non-ccRCC and degree of CAIX expression
- Concomitant medications
- Adverse event monitoring

## 7.6 Post-Imaging Visit (Day 42 ± 7 days p.a.)

All patients will have a visit on Day 42 ± 7 days p.a., irrespective of their nephrectomy and if feasible, which will include the following examinations/procedures:

- Vital signs

- Concomitant medications
- Adverse event monitoring
- HACA testing
- Pregnancy test from urine (for premenopausal female patients)

## **7.7 Final Study Visit**

The final study visit will be conducted depending on the nephrectomy date.

It is expected that most patients will have their partial or total nephrectomy scheduled between 28 and 90 days p.a. (see Section 7.7.2).

A minor proportion of patients is expected to have a scheduled nephrectomy early after administration of Zr-TLX250, i.e. within 28 days p.a. (see Section 7.7.1).

### **7.7.1 Final Study Visit, if Surgery ≤ 28 Days p.a. (Day 42 ± 7 Days p.a.):**

For patients who had their nephrectomy scheduled within 28 days p.a., the visit on Day 42 ± 7 days p.a. will serve as the final study visit and the following assessments will be done in addition to the ones described in Section 7.6 on the same day:

- Physical examination
- Haematology
- Serum chemistry
- Urinalysis (Dipstick)

### **7.7.2 Final Study Visit, if Surgery >28 Days p.a. (35 ± 7 Days after Surgery)**

For patients whose nephrectomy was scheduled between 28 and no longer than 90 days p.a., the final study visit will be at 35 ± 7 days *after surgery*, and the following assessments will be performed.

- Physical examination
- Vital signs
- Haematology
- Serum chemistry
- Urinalysis (Dipstick)
- Concomitant medications

- Adverse event monitoring
- HACA testing

## **8 Procedures and Variables**

Patients will provide written informed consent before any study-related procedures can be performed (see Section 13.2).

Patient-related events and activities including specific instructions, procedures, concomitant medications, dispensing of study drug, and descriptions of AEs are to be recorded in the appropriate source documents and eCRFs.

The schedule of assessments is provided in Table 1. Unless otherwise specified, all examinations and procedures will be performed by the investigator or other regular study personnel.

An additional visit can be scheduled at any time if the investigator considers it necessary.

### **8.1 Baseline Characteristics**

It is anticipated to recruit 252 evaluable male or female patients  $\geq$  18 years with evidence of an IRM scheduled for partial or total nephrectomy (see Section 4.2).

#### **8.1.1 Demographic Characteristics**

The following demographic characteristics will be recorded:

- date of birth or age, depending on local EC requirements
- weight, height, ethnic origin

#### **8.1.2 Medical and Surgical History, Baseline Findings**

Medical/surgical history and medical conditions present before the administration of Zr-TLX250 will be recorded at the screening visit and pre-dose on Day 0.

Detailed instructions on the differentiation between (i) medical / surgical history and (ii) baseline findings can be found in Section 8.8.1.1.

The patients should have a sufficient life-expectancy to justify nephrectomy (see Section 4.2).

#### **8.1.3 Prior and Concomitant Medication**

Prior and concomitant medication will be recorded on the eCRF from screening and throughout the study, beginning on Day 0, until the EOS visit (see Section 6).

The following concomitant medication should not be recorded on the eCRF:

- Anaesthetics, analgesics, sedatives and laxatives given in routinely used regimen and dosage in connection with nephrectomy

#### **8.1.4 Pre-baseline Morphological Imaging**

Patients with suspected ccRCC, typically receive abdominal MRI or CT with and without contrast agent as part of their initial diagnostic work-up. Contrast enhanced MRI or CT is also the standard for re-staging in patients after initial therapy. The imaging methodology will be conducted according to the institutional routine practise.

Pre-baseline images will be collected for evidence of a single indeterminate renal mass (IRM) and for precise volumetric tumour delineation.

[figure not shown]
A current contrast-enhanced abdominal MRI or equivalent standard of care imaging (based on national standards) with contrast agent, not older than 90 days on Day 0, but conducted before any screening procedure, should be available, providing evidence of a newly diagnosed, single renal mass, confined to the kidney, and measuring  $\leq 7$  cm in greatest diameter (stage cT1) (inclusion criterion). Ultrasound images will not be acceptable.

In the scope of this clinical study, no contrast-enhanced CT or MRI will be performed.

Lesions of interest will be spatially localised by the site and independently by the central image readers. The central image readers will not have access to the spatial localisation determined by the site. For lesions located within the kidney, spatial localisation should be conducted as follows

- Definition of the diseased kidney (left or right)
- Definition of the segment within the kidney containing the lesion. The segments are based on Figure 2
- In the event of a total nephrectomy the pathologist should specify the segment location that was used to provide the tissue samples used for central analysis

**Figure 2 Overview of kidney segments for spatial localisation**

From: Gray's Anatomy, 40th Edition, chapter 74, Figure 12

For patients with extra-renal disease the location of the lesion used to obtain the sample should be described by the pathologist. The independent image reviewers will define the image location of interest for extra-renal lesions in a blinded fashion.

### 8.1.5 Pregnancy Tests and Assessment of Postmenopausal Status

Part of the blood samples taken for the clinical laboratory tests at screening will be used to perform a serum  $\beta$ -HCG pregnancy test in women of childbearing potential. On Day 0, a urine pregnancy test will be performed within 24 hours before administration of study drug to confirm the negative pregnancy result from screening. Furthermore a urine pregnancy test will be performed on Day 42  $\pm$  7 days p.a.

In postmenopausal women < 55 years a permanent postmenopausal status must be proven through history of hysterectomy or hormone analysis in serum, with estradiol < 20 pg/mL and follicle stimulating hormone FSH < 40 IU/L, or last spontaneous bleeding at least 2 years before start of the study.

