## Clinical Study Protocol

Zr-TLX250-003

Version: 8.0

Date: 01-Apr-2022

Table 1 Schedule of Study Assessments

Zr-girentuximab (Zr-TLX-250) for PET/CT Imaging of ccRCC (ZIRCON Study)

Examination/Evaluation	Pre-screening	Screening	Study Period						Final Study Visit				
	Pre-BL	BL	Treatment						Imaging	Surgery	Post-imaging Study Visit	If surgery within 28 days p.a.	If surgery 28 to 90 days p.a.
Time point	Pre-BL	BL	0										
Days	-90 to -1	-30 to -1	0						5±2**	90***	42±7	42±7	35±7 post surgery
Hours*			Pre-dose	dosing	0.5	1	2						
Abdo MRI with contrast or equivalent imaging A	x												
Informed consent		x											
Review Inclusion/Exclusion criteria		x											
General													
Medical history / Interim history		x	x										
Physical Exam		x									x	x	
Vital Signs		x	x		x	x	x			x		x	
Haematology & Serum Chemistry H		x	x					x			x	x	
Urinalysis (Dipstick) H		x	x					x			x	x	
Pregnancy Test B		x	x							X			
12 lead ECG		x	x				x						
 Zr - girentuximab PET/CT imaging													
 Zr girentuximab administration				x									
Abdominal PET/CT C								x					
Whole Body PET/CT D								x D					
Standard of truth determination													
Pre-scheduled nephrectomy (SoC) E									←→	x			
Central histology									←→	x			
Safety													
Concomitant medications		x	x	←→	←→	←→	←→	←→	x	x	x	x	
Baseline findings / adverse events		x	x	←→	←→	←→	←→	←→	x	x	x	x	
Anti-drug antibody / HACA blood draw G		x								x		x	

\*) hours post administration (p.a.)

\*\*) not sooner than 72 hours p.a.

\*\*\*) any time after imaging visit, but no later than 90 days p.a.

(A) Evidence of an indeterminate renal mass (IRM). MRI or equivalent standard of care imaging with contrast agent from within 3 months (90 days) of D0 is acceptable; ultrasound is not acceptable.

(B) Pregnancy test for pre-menopausal female patients at baseline, and re-test with urine pregnancy test pre-dose (within 24 hours before dosing) and on day 42 ±7.

(C) Abdominal PET + low dose CT to be conducted for all patients

(D) In case of unexpected evidence of disseminated disease (N1, M1) on imaging, patients may receive an additional whole body PET/CT from skull base to mid-thigh for complete staging at the discretion of the investigator.

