## Clinical Study Protocol

### Zr-TLX250-003

Version: 8.0  
Date: 01-Apr-2022

- Day 0 pre-dose
- Day 5 ± 2 days
- Final study visit: Day 42 ± 7 days p.a. (for patients with nephrectomy ≤ 28 days p.a.)
- Final study visit: 35 ± 7 days after surgery (for patients with nephrectomy > 28 days p.a.)

Laboratory assessments will be performed by a central laboratory. Because of the potential for radioactivity in some blood samples, the laboratory must adhere to their SOPs and/or any guidance and regulations for handling radioactive substances.

Samples will be tested for the following parameters:

**Haematology:** haemoglobin, haematocrit, mean corpuscular volume (MCV), mean corpuscular haemoglobin (MCH), white blood cell count (total and differential: leukocytes, neutrophils, eosinophils, basophils, lymphocytes, monocytes), red blood cells, platelets

**Biochemistry:** sodium, potassium, chloride, calcium, glucose, creatinine, urea, albumin, total bilirubin, aspartate transaminase (AST), alanine transaminase (ALT), alkaline phosphatase, gamma-glutamyl transferase (GGT), lipase, amylase, total protein

**Clotting status:** prothrombin time (quick), reagent-independent prothrombin ratio (international normalised ratio; INR), activated partial thromboplastin time (aPTT).

**Immunogenicity:** HACA.

**Urinalysis:** density, pH, protein, glucose, blood, urobilinogen, erythrocytes, leukocytes, ketones, bilirubin, nitrite.

A serum β-HCG pregnancy test will be performed only in premenopausal women at screening. Confirmation of the negative result will be done with a urine pregnancy test within 24 hours before administration of the study drug on Day 0 and at the Day 42 (± 7 days) time point (see Section 8.1.5).

The investigator will sign each laboratory assessment to confirm review of the results. Clinically relevant values have to be highlighted as “c.s.” (“clinically significant”). The results will be sent back to the investigational sites and be included in the patient’s eCRF.

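### Protocol section 8.1.5 has the FSH limit reversed: low rather than high FSH counts as proof of menopause in women under 55 (minor, safety wording)

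*Protocol*

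**What the plan says.** Protocol section 8.1.5 has two parts. The first assigns the serum test at screening to women of childbearing potential, followed by urine tests within 24 hours before dosing and at Day 42 ± 7. The second states how permanent postmenopausal status is to be proven in a woman under 55 who is regarded as postmenopausal. There are three routes, joined by 'or':

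- a history of hysterectomy;
- "hormone analysis in serum, with estradiol < 20 pg/mL and follicle stimulating hormone FSH < 40 IU/L";
- a last spontaneous bleed at least 2 years before the study starts.

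Menopausal status then appears wherever the tests are scheduled:

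- Section 8.8.3 says of the serum β-HCG test that the "pregnancy test will be performed only in premenopausal women at screening", and refers back to section 8.1.5.
- Table 1, footnote B: "Pregnancy test for pre-menopausal female patients at baseline, and re-test with urine pregnancy test pre-dose (within 24 hours before dosing").
- Section 7.2 (screening): "Pregnancy test from serum (for premenopausal female patients").
- Section 7.3.1 (pre-dose): "Pregnancy test from urine (for premenopausal female patients) within 24 hours before administration".
- Section 7.6 (Day 42): "Pregnancy test from urine (for premenopausal female patients").

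Other places use childbearing potential instead: inclusion criterion 5, the study design part of the synopsis, and the first part of section 8.1.5. Neither document defines that term. Section 8.1.5 is the only rule on menopausal status in either document, and no other FSH limit is given.

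**The concern.** After menopause ovarian estradiol falls, negative feedback is lost and FSH rises. A hormonal proof of menopause therefore needs an upper limit on estradiol and a lower limit on FSH. Section 8.1.5 sets two upper limits. The routes are alternatives, so the faulty one is sufficient alone.

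What is at stake is whether a pregnancy test is done before dosing. Pregnancy is exclusion criterion 11, and section 1.3 puts the effective dose of the administration at about 18.0 to 20.5 mSv, depending on the dosimetry method. A woman under 55 classed as permanently postmenopausal on the wrong hormone pattern falls outside the premenopausal wording that triggers the tests in sections 7.2, 7.3.1 and 8.8.3.

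**Working it through.** The plan gives no figure to reproduce. The check is of the logic of the rule and of where its result is used.

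**Inputs.** The three routes, their 'or', and the 'and' between the two hormone limits come from section 8.1.5. The testing rules come from Table 1 footnote B and sections 7.2, 7.3.1, 7.6 and 8.8.3. The direction of the FSH change is ordinary physiology. The 40 IU/L cut-off is the protocol's own and is not disputed.

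**Rule as written.** Proven = hysterectomy OR (E2 < 20 AND FSH < 40) OR last bleed at least 2 years ago.

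**Rule with the sign corrected.** Proven = hysterectomy OR (E2 < 20 AND FSH > 40) OR last bleed at least 2 years ago.

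The hormone route decides the outcome only when there has been no hysterectomy and the last bleed was within 2 years. Setting aside FSH of exactly 40, four combinations remain:

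| E2 (pg/mL) | FSH (IU/L) | As written | Corrected | Effect of the error |
|---|---|---|---|---|
| < 20 | < 40 | proven | not proven | tests could be omitted |
| < 20 | > 40 | not proven | proven | extra tests only |
| ≥ 20 | < 40 | not proven | not proven | none |
| ≥ 20 | > 40 | not proven | not proven | none |

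The rules differ in two combinations, and one of those is in the unsafe direction. This counts logical cases and says nothing about how often each occurs.

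**Tests affected.** Three pregnancy tests are planned: screening serum, pre-dose urine and Day 42 urine. The Day 42 test follows dosing and cannot prevent exposure, so 3 − 1 = 2 tests are relevant.

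**What the missed tests would have covered.** Estradiol below 20 pg/mL makes an established pregnancy unlikely at the time of sampling. A very early pregnancy, or conception after the sample, remains possible. Section 8.1.5 sets no date for the hormone sample. Section 7.2 states: "Screening is to take place between 30 days and 1 day before (-30 days to -1 day"). If the sample is taken in that window, it precedes dosing by 1 to 30 days. The urine test within 24 hours before dosing is the one that closes this interval.

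**How many women.** Six conditions must hold together: age under 55, regarded as postmenopausal, no hysterectomy, a bleed within 2 years, estradiol < 20 pg/mL, and FSH < 40 IU/L. Two more are needed before a test is lost. Someone must order the hormones, which are not scheduled: they are absent from Table 1, the screening list in section 7.2, the laboratory panel in section 8.8.3 and the blood-volume table (Table 4). The site must also treat the result as removing the need for a test. That makes 6 + 2 = 8 conditions. The documents give no count of such women.

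**The case against.** The strongest reply is that testing is also required elsewhere on a different basis. Inclusion criterion 5, the synopsis and the first part of section 8.1.5 itself all tie the tests before dosing to childbearing potential. On that reading, a site would have to let the shorter wording of the procedure lists override an eligibility criterion, and no section says that proof of menopause waives a test. This is a fair point and it limits the consequence. It does not remove it, because childbearing potential is undefined and section 8.1.5 is the only rule a site could turn to when deciding it.

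The case is also remote. It needs an investigator to call a woman postmenopausal although she bled within 2 years and has a low FSH. Harm further needs conception despite the contraception that inclusion criterion 8 asks patients to accept until at least Day 42. This stands, and it is why the point is minor.

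Clinicians may simply recognise a slip and apply the correct direction. Probably many would. But sections 3.4 and 12.1 require close adherence to the protocol, so a site that did so would be departing from its text.

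Finally, the point rests on one character in text read from a PDF by a program. A misreading cannot be fully excluded, though nothing suggests one and the other inequality signs in the sentence make sense. It is worth a glance at the source page.

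**Conclusion.** The concern holds as a minor drafting error in safety wording. The FSH inequality in section 8.1.5 is reversed, and nothing else in either document corrects it. Confidence in the direction is high, subject to the source page reading as extracted.

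The practical effect is small: very few women, possibly none, each of whom could miss up to two pregnancy tests before dosing. That effect is inferred from the premenopausal-only wording and assumes a site uses section 8.1.5 to decide who is tested. Sensitivity, specificity, sample size, power and the analysis are untouched.

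**What to change.** In section 8.1.5, change the FSH limit to FSH > 40 IU/L and leave the estradiol limit as it is. Until that is in force, instruct sites not to omit any pregnancy test on the strength of the hormone route.

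The text change is one character, and the interim instruction costs at most a few inexpensive pregnancy tests. There is no effect on accrual or analysis. The administrative cost may be larger than the edit suggests. Section 3.4 requires a formal amendment for anything not purely administrative, which probably includes this threshold, and the study runs in nine countries. Version 8.0 is dated April 2022 and the synopsis plans the end of recruitment for Q3/2022, so the interim instruction may do most of the work. The correction still matters for any later protocol that reuses this section.

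Replacing the premenopausal wording with childbearing potential in sections 7.2, 7.3.1, 7.6 and 8.8.3 and in Table 1 footnote B would be tidier, but is not needed once the sign is right.
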